## 9.3 Recording and reporting of AEs and SAEs

All AEs and SAEs occurring from the time of **start of trial treatment** until the end of the trial will be reported by participants using an online form. Participants will be prompted to enter any details of events at each login event (quarterly) and encouraged to report any event proactively using the online form or by contacting the study team by telephone and email. All AEs will be logged in REDCap Cloud.

Receipt of an AE or SAE on the system will prompt review by the study team. AEs will be reviewed by at least two members of the TMG. SAEs will be reviewed by a study clinician within

24 hours. The participant, and their GP where appropriate, will be contacted for follow-up and recommended action. The Sponsor will also be informed.

AE and SAE actions and monitoring will be recorded electronically, including the following information

- full details in medical terms and case description
- event duration (start and end dates, if applicable)
- action taken
- outcome
- seriousness criteria
- causality (i.e. relatedness to trial drug / investigation), in the opinion of the investigator
- whether the event would be considered anticipated.

Any change of condition or other follow-up information will be faxed to the Sponsor as soon as it is available or at least within 24 hours of the information becoming available. Events will be followed up until the event has resolved or a final outcome has been reached.

#### Absent participant follow-up

In the event that a participant who has entered the intention-to-treat cohort fails to complete any online activity on two consecutive timepoints they will be contacted by telephone by a study administrator. The purpose of the call will be to verify the health and wellbeing of the participant. If any suspected AE is detected this will prompt an AE report.

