### 3.7 Table of endpoints/outcomes

Objectives	Outcome Measures	Timepoint(s) of evaluation of this outcome measure (if applicable)
Primary Objective To compare the effect of vitamin D supplementation on executive function	Trails-B measure, completed in one session online on the PROTECT website.	Baseline, six, 12, and 24 months Primary endpoint is 24 months
Secondary Objectives To compare the effect of vitamin D supplementation on cognition, function and behaviour  To establish the cost-effectiveness of vitamin D supplementation	Cognitive Test Battery (Paired Associate Learning, Digit Span, Self-Ordered Search Task [working / spatial memory tasks], Switching Stroop and Baddeley Grammatical Reasoning [Executive Function Tasks  Instrumental Activities of Daily Living Scale  Mild Behaviour Impairment Scale  EQ5D scale	Baseline, six, 12, and 24 months
Tertiary Objectives Example: To monitor safety and compliance of vitamin D supplementation in the trial cohort  To explore participant experience of taking part in an online trial	Adverse Event and Serious Adverse Event reporting in response to email prompts, or proactively by participants through the website, telephone or email  Anonymous survey	Quarterly  24 months (after study completion)

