### 7.7 Trial assessments

Assessments will be conducted at baseline, 26, 52, and 104 weeks. Participants will receive weekly automated emails notifying them that assessments are available to complete until they are completed or no longer available. The assessments will become available for completion two weeks before the assessment point and remain open for completion during the week of the assessment point and a further five weeks, making them available for eight weeks in total. Missing data or late data will be accounted for within the analysis plan.

Assessments will follow the set online assessment protocol described below.

1. scale Trail-making B (primary outcome measure)
2. PROTECT Cognitive Tests: Switching Stroop Test, Baddeley Grammatical Reasoning , Self-ordered Search, Digit Span, and Paired Associate Learning Tasks (secondary outcome measures)
3. Instrumental Activities of Daily Living
4. EQ5D measure of health and wellbeing
5. Mild Behaviour Impairment Scale

An anonymous survey will be completed at the end of the study to provide a process measure and to capture participant experience.

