## 7.12 End of trial participation

End of trial is defined as the last assessment point completed by the last participant to enrol in the study or six weeks after the last participant's last time point if the last assessments are not completed.

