### 8.11 Assessment of compliance with treatment

**Compliance Monitoring:** Monitoring of participant use of the tablets will be achieved through a 'medication diary' on the PROTECT site which will ask participants to provide a quarterly tablet count, both of which will be entered online. This will also be supported through reminder emails and regular newsletters from the PROTECT study. This process is anticipated to be highly effective. However, since it is reliant on participant adherence and fidelity, an additional sub-group of compliance testing will also be performed (see below).

**Sub-group Compliance Monitoring:** In addition a sub-group of 10% of the total cohort (n = 58) will be recruited to complete a finger prick test to analyse blood levels of Vitamin D3 metabolites at baseline and primary endpoint (24 months) as a further compliance measure. This process will be delivered through partnership with the Sandwell and West Birmingham NHS foundation Trust test facility. This process will involve:

- Sub-group compliance participants allocated to the first 10% of randomised participants
- Study administrator attaches participant identifier label to test kit and posts kit to participant
- Participants will receive a test kit to complete at home, involving a short finger prick test
- Participants use pre-addressed envelope to send their completed test to the Sandwell and West Birmingham NHS Foundation Trust test laboratory
- Laboratory completes Vitamin D3 analysis according to published protocols using anonymised sample identifiers. No sample is retained after analysis
- Laboratory returns anonymised test results to study team

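### The welfare call needs two consecutive missed timepoints, which section 9.3 does not define; on either reading, silence that starts late in treatment never triggers a call

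*Protocol*

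**What the plan says.** Reporting is by participants. Under section 9.3 of the protocol, AEs and SAEs from the start of treatment "until the end of the trial will be reported by participants using an online form". Telephone and email are also open, but again to the participant. Section 9.2 makes hospitalisation, death and life-threatening conditions the operational SAE criteria.

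The back-stop is the paragraph on absent participants in section 9.3. It applies within the intention-to-treat population: if someone "fails to complete any online activity on two consecutive timepoints they will be contacted by telephone by a study administrator". Its aim is to check on their health, and a suspected AE found in this way prompts a report. The word *timepoints* is not defined there.

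Two schedules could be meant:

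- Assessments. Section 7.7: "Assessments will be conducted at baseline, 26, 52, and 104 weeks". Each opens two weeks early and stays open for the due week and five more, "making them available for eight weeks in total".
- Quarterly logins. Section 9.3: "Participants will be prompted to enter any details of events at each login event (quarterly". Section 8.11 asks participants to "provide a quarterly tablet count, both of which will be entered online". In the table in section 3.7, the timepoint column reads Quarterly against "Adverse Event and Serious Adverse Event reporting in response to email prompts".

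Section 7.12 ends the trial at the last enrolled participant's final completed assessment, or "six weeks after the last participant's last time point if the last assessments are not completed".

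**The concern.** A participant who has died or lost capacity cannot fill in a form, and the protocol names no relative, GP or record source as an alternative reporter. The 24-hour clinician review of SAEs in section 9.3 starts only when a report arrives. The welfare call is therefore what separates a death from an ordinary lapse in logging in.

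A rule that needs two consecutive misses cannot act when only one timepoint remains. How long that blind stretch lasts depends on a word the protocol leaves open, so two administrators could apply the rule differently.

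Two things are at stake. Monitoring safety is a stated objective (section 3.7), and deaths and incapacitating SAEs late in treatment may be missing from what the Trial Management Group reviews. Also, the primary analysis in section 10.3 uses those with complete week-104 data, and a secondary analysis imputes outcomes on the assumption that data are missing at random. Without the reason for a missing week-104 assessment, neither is easy to judge.

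**Working it through.** **The plan's own figure.** The assessment window is 2 + 1 + 5 = 8 weeks, as section 7.7 states.

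**Other checks after treatment starts.** None covers a participant who goes silent later:

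- The compliance call in section 7.8 is made at one week only.
- The capacity algorithm in section 7.8 works on completed tests at two consecutive assessments, so it cannot see someone who has stopped.
- Assessment reminders in section 7.7 are automated emails.

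**Rule applied to the schedule.** Take timepoints t(1) < … < t(k). Assume a participant completes everything up to some moment and is then permanently silent. If silence starts between t(j) and t(j+1), the second consecutive miss is at t(j+2). If silence starts after t(k−1), there is no second miss and no call. The uncovered stretch is therefore t(k) − t(k−1).

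| | Quarterly logins | Assessments |
|---|---|---|
| Timepoints (weeks) | 13, 26, 39, 52, 65, 78, 91, 104 (exact weeks assumed) | 26, 52, 104 |
| Uncovered stretch | 104 − 91 = 13 weeks | 104 − 52 = 52 weeks |
| Share of 104 weeks | 13/104 = 12.5% | 52/104 = 50% |
| Wait from silence to second miss, where there is one | about 13 to 26 weeks | about 26 to 78 weeks |

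**Examples.**

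- Silence from week 60: second miss at week 78 on the quarterly reading; no call on the assessment reading.
- Silence from week 80: second miss at week 104 on the quarterly reading; no call on the assessment reading.
- Silence from week 92 or week 100: no call on either reading.

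**Window tail.** A missed assessment is established only when its window closes. For week 104 that is about week 109 to 110. On the assessment reading, someone silent from week 27 would be called at about week 110, which is 110 − 27 = 83 weeks later. For the last participant enrolled, the trial ends six weeks after the final time point, 104 + 6 = week 110, so a call triggered then has almost no time left.

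**Exception.** The uncovered stretch applies only to those who completed the timepoint before last. On the assessment reading, a participant who had already missed week 52 and falls silent at week 80 does meet the trigger at week 104. So does one who had not yet completed week 52 and falls silent while its window is still open.

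**The case against.** The strongest reply is that the quarterly reading fits the text better. The rule speaks of any online activity, not of assessments. It sits in the section that has just described quarterly logins, tablet counts are quarterly and online, and the timepoint column in section 3.7 includes Quarterly. Section 7.8 also uses the term for the one-week call, which is not an outcome assessment. This largely stands. A reader might infer that nothing after week 52 can trigger a call and that half of treatment is unmonitored. The protocol does not support that as a general statement. It holds only on the assessment reading, and there only for those who completed week 52. Section 7.12 does tie the term to assessments, so the ambiguity is real, but it does not settle in that direction.

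A reader might also apply these shares to the 20% drop-out allowance in section 10.1 to count uncalled participants. That does not work. The allowance is a planning figure that does not separate silent loss from withdrawals the team knows about, and nothing says that loss is spread evenly over time. No death or incapacity rate is given either, so the number of missed SAEs cannot be sized.

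Most people who are hospitalised recover and can report at the next prompt, and relatives may volunteer information. This stands too: the gap concerns death and lasting incapacity.

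The two-miss rule is a reasonable filter against lateness. With 584 × 8 = 4,672 login occasions, calling after every single miss would mean about 234 to 467 calls at an assumed miss rate of 5% to 10%. That is a reason to keep the filter, not a reason to leave the end of treatment uncovered.

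Finally, section 9.4 mentions a Trial Monitoring Plan that is not at hand and might specify close-out contact. If it does, the protocol should say so.

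**Conclusion.** The point holds in a limited form. Section 9.3 leaves *timepoints* undefined and states no closing contact for someone who misses only the last one. On either reading, silence late in treatment goes unchecked: from about week 91 if timepoints are quarterly logins (about 13 of 104 weeks), or from a completed week-52 assessment if they are assessments (up to 52 of 104 weeks). The 50% share and the delay of about 83 weeks belong to the assessment reading alone.

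This assumes logins every 13 weeks, permanent silence, earlier timepoints completed and nobody else reporting the event. Defining the term alone would shorten the gap but not close it, because the last interval stays uncovered. Late deaths and incapacitating SAEs may be recorded as non-completion; how many cannot be derived from the protocol. It should be corrected, because these are the events that self-report cannot capture.

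**What to change.** In section 9.3:

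1. State that *timepoints* in the absent-participant rule means the quarterly logins, and keep the requirement of two consecutive misses.
2. Add one closing call by the study administrator, before safety data are locked, to every non-withdrawn participant who has not completed the last quarterly login or the week-104 assessment. Record vital status, hospitalisation and, where it can be learned, the reason for the missing assessment.
3. Check that the end-of-trial definition in section 7.12 leaves time for these calls for the last participant enrolled.

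The cost is a short wording change and a modest number of calls by staff who already make them, some of them to people who are merely late. If missing week-104 assessments stay within the 20% allowance in section 10.1, that condition gives at most about 117 calls (584 × 0.20 = 116.8). Formal withdrawals reduce this; participants who missed only the last login add to it.

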## 9.4 Responsibilities

### Principal Investigator (PI), Trial Coordinator and clinical delegate (TMG member):

Initial review of any AEs when reported by a participant

1. Using medical judgement in assigning seriousness, causality and whether the event/reaction was anticipated
2. Ensuring that all SAEs are recorded and reported to the sponsor within 24 hours of becoming aware of the event and provide further follow-up information as soon as available. Ensuring that SAEs are chased with Sponsor if a record of receipt is not received within 2 working days of initial reporting.
3. Ensuring that AEs and ARs are recorded and reported to the sponsor in line with the requirements of the protocol.
4. Central data collection and verification of AEs and SAEs
5. Reporting safety information to the oversight committees identified for the trial (Trial Management Group) according to the Trial Monitoring Plan.
6. The unblinding of a participant for the purpose of expedited reporting

### Trial Management Group (TMG):

In accordance with the Trial Terms of Reference for the TSG, periodically reviewing overall safety data to determine patterns and trends of events, or to identify safety issues, which would not be apparent on an individual case basis.

## 10 STATISTICS AND DATA ANALYSIS

### 10.1 Sample size calculation

The sample size calculation is based on a published study of online cognitive training in adults over 50, which showed significant change in executive function in adults with AACD (Corbett, et al. 2015b). Based on an effect size of 0.3, which is clinically meaningful and has been achieved through similar trials in this field, 234 participants would be required for each group to provide 90% power at a two-sided 0.05 significance level and assuming a conservative drop-out rate of 20%. Therefore, a total of 584 participants (293 per group) will be recruited.

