#### 4 TRIAL DESIGN

A two-year two-arm placebo-controlled double-blinded randomised controlled trial in 584 participants.

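### Protocol section 10.1 gives a recruitment target of 584 in total and 293 per group, but two groups of 293 make 586; the drop-out clause is also attached to the wrong number

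*Protocol*

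**What the plan says.** Section 10.1 (Sample size calculation) takes a standardised effect, "Based on an effect size of 0.3, which is clinically meaningful", and says that "234 participants would be required for each group to provide 90% power", with a two-sided 0.05 significance level. The same sentence goes on to say that this is "assuming a conservative drop-out rate of 20"%. The next sentence, opening with *Therefore*, concludes that "a total of 584 participants (293 per group) will be recruited".

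Section 4 (Trial Design) describes a two-arm, "placebo-controlled double-blinded randomised controlled trial in 584 participants". Section 8.11 sets the finger-prick compliance sub-group at 10% of the cohort and gives it as 58.

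No section states an unequal allocation. Section 10.1 gives a single per-group figure for both arms, which implies 1:1. Neither 586 nor 292 per group appears anywhere in the protocol.

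**The concern.** Two things are wrong in the paragraph.

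- **The total and the per-group figure disagree.** They stand in the same sentence of the current version. With two equal groups, only one of them can be the target.
- **The drop-out clause is in the wrong place.** Read literally, the sentence says that 234 per group already allows for 20% loss. By the protocol's own inputs, 234 is the number that must be evaluable, before any allowance.

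The sample size is a basic design figure that is normally carried into the final report. Section 10.3 restricts the primary analysis to participants with complete data at week 104, so the number recruited and the number evaluable need to be clearly separated. If the figures were badly wrong, the stated power would be at stake. The check below shows that it is not.

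**Working it through.** **Inputs, all from section 10.1 unless noted:** effect size d = 0.3; power 90%; two-sided α = 0.05; drop-out 20%; two arms (section 4); equal allocation (implied, not stated).

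**1. Reproduce the 234.** The normal formula for two means with standardised effect d is

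n per group = 2(z₀.₉₇₅ + z₀.₉₀)² / d² = 2(1.9600 + 1.2816)² / 0.09 = 233.5, rounded up to **234**.

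The two-sample t-test gives 234.46. No drop-out enters either calculation, so 234 is the evaluable number.

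**2. Reproduce the 293.** 234 / (1 − 0.20) = 292.5, rounded up to **293** per group. The allowance for drop-out enters here.

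**3. The total.** 2 × 293 = **586**, not 584. Inflating the total directly gives 468 / 0.8 = 585, which is also not 584 and becomes 586 in equal groups. The stated 584 is 2 × 292. It can be reached by inflating the unrounded figure: 233.5 / 0.8 = 291.9, rounded up to 292. That is a possible origin of the mismatch, but the protocol does not say so.

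**4. Other readings of the inputs.** None explains the figures: one-sided α gives 191 per group, 80% power gives 175, and multiplying 234 by 1.2 instead of dividing by 0.8 gives 281.

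**5. Effect on power,** with 20% loss in each group:

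| Recruited | Per group | Evaluable per group | Power, normal formula | Power, t-test |
|---|---|---|---|---|
| 584 | 292 | 292 × 0.8 = 233.6 | 90.01% | 89.89% |
| 586 | 293 | 293 × 0.8 = 234.4 | 90.11% | 89.99% |
| (required number) | – | 234 | 90.06% | 89.94% |

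The two totals differ by about 0.1 percentage point under either method. The choice of formula matters as much: by t-test the protocol's own 234 is also fractionally under 90%.

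**6. Effect on the 10% sub-group (section 8.11).** 10% of 584 is 58.4 and 10% of 586 is 58.6, so the stated 58 changes by at most one person.

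**The case against.** The strongest reply is that nothing of substance is wrong. The figures 234 and 293 both reproduce. The word *Therefore* and the rise to 293 show that the second sentence is the inflation step, so a careful reader recovers the intended order. By the formula that yields 234, a total of 584 with 20% loss still gives 90% power. The shortfall against 234 is 0.4 of a participant, which is rounding. The primary model in section 10.3 also adjusts for baseline score, which the calculation does not credit.

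All of this stands, and it limits the weight of the point. It does not remove the contradiction: 584 and 293 per group are both stated as what will be recruited, and they do not agree.

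A reader might also infer more than the text supports:

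- **That power is really about 82.5%.** If 234 per group were recruited and 20% lost, 234 × 0.8 = 187.2 would remain, with power of 82.5% by t-test (82.7% by normal formula). The protocol nowhere proposes recruiting 234 per group; it labels that number as required and 584 (293 per group) as the number to be recruited.
- **That the target could be any of 234, 292 or 293 per group.** The real ambiguity is only 584 against 586.
- **That the 2023 decision to end at two years is undermined.** The amendment history cites power already achieved, but a gap of two participants cannot decide that, and the protocol gives no realised number against which to test it.

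**Conclusion.** The point holds as a minor correction. Section 10.1 states a recruitment total that does not match its own per-group figure, by two participants (2 / 586 = 0.3%), and places the drop-out assumption on the evaluable number instead of on the step that inflates it. The second fault is one of wording, not of calculation.

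The effect on power is about 0.1 percentage point. There is no material effect on the compliance sub-group or on the decision to shorten the trial. It would be wrong to conclude that the trial is underpowered on account of this discrepancy.

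The conclusion assumes equal allocation, which the single per-group figure implies, and an unadjusted two-group comparison of means, which reproduces the stated 234.

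**What to change.** Restate section 10.1 in one of two ways:

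- **Preferred:** 234 evaluable participants per group give 90% power; allowing for 20% drop-out, 293 per group (586 in total) will be recruited. Change the total in section 4 to 586, and check the sub-group number in section 8.11 (58.6 before rounding).
- **Alternative:** keep 584 and write 292 per group, with about 90% power after 20% drop-out. Section 4 and the sub-group of 58 then stand as they are.

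In either version, move the drop-out clause so that it qualifies the number recruited and not the 234.

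The cost is a change of wording. No analysis changes, and keeping 584 gives up about 0.1 percentage point of power relative to 586.

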## 10.2 Planned recruitment rate

Based on recruitment to trials previously delivered through PROTECT we anticipate a recruitment rate of at least 300 per month. A three-month recruitment window has been defined but will be extended following recruitment review if required.

